PROTOCOL

Acceptability, feasibility and impacts of remote symptom monitoring and automated treatment plans in children with Cystic Fibrosis (CF) on highly effective modulators: a pilot randomised controlled trial.

HREC #: 91117

Protocol Version and date:
Version 2 28/10/2022

Document history:

Version Number and Date	Summary of changes
Version 1 26.10.2022	Initial submission
Version 2 28.10.2022	Re-submission 1 to address ethics queries

Statement of Compliance

This clinical trial will be conducted in compliance with all stipulation of this protocol, the conditions of the ethics committee approval, the NHMRC National Statement on ethical Conduct in Human Research (2007 and all updates), the Integrated Addendum to ICH E6 (R1): Guideline for Good Clinical Practice E6 (R2), dated 9 November 2016 annotated with TGA comments and the NHMRC guidance Safety monitoring and reporting in clinical trials involving therapeutic goods (EH59, 2016).

PROTOCOL SYNOPSIS

TITLE	Acceptability, feasibility and impacts of remote symptom monitoring and automated treatment plans in children with Cystic Fibrosis (CF) on highly effective modulators: a pilot randomised controlled trial.
STUDY DESCRIPTION	This is a pilot randomised controlled trial with participants randomly allocated to remote symptom monitoring and automated treatment plan care model (intervention group) versus usual hospital CF care (control group). The two models of care will be compared and the feasibility and acceptability of the new model of care will be assessed.
OBJECTIVES	
Primary:
 
 1. To assess the uptake and feasibility of the remote monitoring and automated treatment plans 2. To assess the impact and acceptability of the remote system monitoring and automated treatment plans on family experience 3. To assess the impact and acceptability of the remote system monitoring and automated treatment plans on CF multidisciplinary team (MDT) experience 
Secondary:
 
 1. To understand changes in outcome measures over time between the two groups in children on highly effective modulators 2. To assess the cost-effectiveness of the remote monitoring and automated treatment plans compared to usual care by undertaking a health economic evaluation from healthcare and societal (family) perspectives.
OUTCOMES AND OUTCOME MEASURES	
 1. To assess the uptake and feasibility of the remote monitoring and automated treatment plans 
 a. Number of symptom surveys completed (retention of participants and survey completion rate) b. Number of tasks completed c. Number of contacts between CF team and family (staff workload) 2. To assess the impact and acceptability of the remote system monitoring and automated treatment plans on family experience 
 a. Semi structured interviews with participants investigating beliefs, acceptability and feasibility of the remote symptom monitoring and automated treatment plan care model b. Overall service satisfaction 3. To assess the impact and acceptability of the remote system monitoring and automated treatment plans on CF MDT experience 
 a. Semi structured interviews with staff investigating beliefs, acceptability and feasibility of the remote symptom monitoring and automated treatment plan care model 4. To understand changes in outcome measures over time between the two groups in children on highly effective modulators 
 a. Change in child lung function (Forced Expiratory Volume in 1 Second, FEV₁) b. Number of detected pulmonary exacerbations c. Antibiotic usage d. Child Quality of Life (measured with the CF Questionnaire Revised, CFQ-R and EQ-5D-Y)

Study Name: Acceptability, feasibility and impacts of remote symptom monitoring and automated treatment plans in children with Cystic Fibrosis (CF) on highly effective modulators: a pilot randomised controlled trial.

Protocol Number: 91117

Version & date: version 2, 28.10.2022

	
5. To assess the cost-effectiveness of the remote monitoring and automated treatment plans compared to usual care by undertaking a health economic evaluation from healthcare and societal (family) perspectives.
 
 a. Number of detected pulmonary exacerbations b. Antibiotic usage c. Number of hospital admissions and ED presentations d. Hospital length of stay e. Travel time and costs for appointments and admissions f. Caregiver time off work & patient time off school to attend appointments/admissions g. Number of contacts between CF team and family
TRIAL POPULATION	
Children with cystic fibrosis on highly effective modulator therapy (either ivacaftor or elexacaftor–tezacaftor–ivacaftor (ETI)) under the care of the Royal Children’s Hospital.
 
Members of the RCH CF MDT

DESCRIPTION OF SITES	The Royal Children’s Hospital (single site)
DESCRIPTION OF INTERVENTIONS	
Intervention group participants will be asked to complete a symptom survey twice a week. Over the course of ensuing 12-months, if the system detects a pulmonary exacerbation is present, families will be asked to complete the symptom survey on a daily basis and will receive an automated treatment plan sent via the electronic medical record informing them of changes to their child’s treatment plan. Control group participants will receive usual care for their child’s CF at RCH which typically involves 4 outpatient clinics per year.

TRIAL DURATION	It is estimated that the trial will be completed in 18 months.
PARTICIPANT DURATION	Participants will be involved in the study for approximately 14 months, including the intervention period of 12 months and baseline and final semi-structured interviews.

GLOSSARY OF ABBREVIATIONS

ABBREVIATION	TERM
CF	Cystic Fibrosis
CFTR	Cystic fibrosis transmembrane conductance regulator
FEV1	Forced expiration in the first minute
CFQ-R	Cystic fibrosis questionnaire revised
ETI	Elexacaftor/tezacaftor/ivacaftor
RCH	Royal Children's Hospital
EMR	Electronic medical record
TGA	Therapeutic goods association
MDT	Multidisciplinary team
QOL	Quality of life
LOS	Length of stay
SPSS	Statistical Package for the Social Sciences

INVESTIGATOR AGREEMENT

I have read the protocol entitled “Remote symptom monitoring and automated treatment plans in children with Cystic Fibrosis”.

By signing this protocol, I agree to conduct the clinical trial, after approval by a Human Research Ethics Committee or Institutional Review Board (as appropriate), in accordance with the protocol, the principles of the Declaration of Helsinki and the good clinical practice guidelines adopted by the TGA [Integrated Addendum to ICH E6 (R1): Guideline for Good Clinical Practice E6 (R2), dated 9 November 2016 annotated with TGA comments].

Changes to the protocol will only be implemented after written approval is received from the Human Research Ethics Committee or Institutional Review Board (as appropriate), with the exception of medical emergencies.

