3 TRIAL OBJECTIVES AND OUTCOMES

3.1 Aims

In a sample of children with CF attending the RCH CF service and on a highly effective modulator, we aim to:

- evaluate the feasibility and acceptability of a remote symptom monitoring and automated treatment plan care model (intervention only)
- understand changes in outcome measures over time between the two groups in children on highly effective modulators; and

Study Name: Acceptability, feasibility and impacts of remote symptom monitoring and automated treatment plans in children with Cystic Fibrosis (CF) on highly effective modulators: a pilot randomised controlled trial.

Protocol Number: 91117

Version & date: version 2, 28.10.2022

- determine the costs to the healthcare system and to families of the remote symptom monitoring and automated treatment plan care model versus usual care.

Hypothesis:

We hypothesise that compared with usual care, the remote symptom monitoring and automated treatment plan care model will:

1. Be an acceptable method of monitoring for families and the CF MDT;
2. Be a feasible method of monitoring for families and CF MDT;
3. Detect more pulmonary exacerbations earlier and enable earlier treatment than usual care; and
4. Be cost neutral compared to usual care.

Objectives:

Primary:

1. To assess the **uptake and feasibility** of the remote monitoring and automated treatment plans (measured as number of symptom surveys completed, and tasks completed);
2. To assess the **impact and acceptability** of the remote system monitoring and automated treatment plans on **family experience** (measured as experience of the program; acceptability of the program);
3. To assess the **impact and acceptability** of the remote system monitoring and automated treatment plans on **CF MDT experience** (measured as experience of the program; acceptability of the program) compared to usual care.

Secondary:

4. To understand **changes in outcome measures** over time between the two groups in children on highly effective modulators
5. To assess the **cost-effectiveness** of the remote monitoring and automated treatment plans compared to usual care by undertaking a health economic evaluation from healthcare and societal (family) perspectives.

Primary and Secondary Objectives	Outcome of Interest	Data Sources	Methods of collection	Period of Data Collection		
				3/12	6/12	12/12
ACCEPTABILITY & FEASIBILITY						

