1. What is the feasibility of the remote monitoring system for families and CF MDT ?	What is the uptake of the remote monitoring and automated treatment plans (number of surveys completed, number of tasks completed, number of contacts between CF MDT and patients)	EPIC EMR	EPIC pre-made reports specific to the trial.	●	●	●
2. What is the CF MDT's experience of the remote monitoring system?	Confidence in system detecting exacerbation, appropriateness treatment initiated, confidence in navigating system and data in EPIC, feasibility/acceptability of the model	MDT semi structured interviews	Qualitative interviews completed via MS Teams	●		●
3. What is the families experience of the remote monitoring system?	Confidence in system detecting exacerbation, appropriateness treatment initiated, confidence in navigating the portal, feasibility/acceptability of the model	Family semi structured interviews	Qualitative interviews completed via MS Teams	●		●
CLINICAL EFFECTIVENESS						
4. What is the impact of remote monitoring on changes in outcome measures over time?	Number of pulmonary exacerbations detected, change in lung function, outpatient clinic visits, hospital admissions and length of stay, antibiotic usage and QOL scores	Trial data from EPIC Family Survey CFQ-R EQ-5D-Y	Chart review and EPIC reports, exacerbation survey & QOL surveys via REDCap	●	●	●
HEALTH ECONOMIC EVALUATION						
5. What is the cost of implementing the model of care? What is the cost effectiveness ?	Costs of conducting the model of care compared to usual care; costs/savings of change in OP/admissions encounters; costs/savings to families compared with accessing usual care.	Trial data and supplementary unit costings	Trial data on the model of care, health service costs, health service use and patient costs and outcomes will be combined with relevant unit costs to produce a cost-effectiveness analysis.	●	●	●

Study Name: Acceptability, feasibility and impacts of remote symptom monitoring and automated treatment plans in children with Cystic Fibrosis (CF) on highly effective modulators: a pilot randomised controlled trial.

Protocol Number: 91117

Version & date: version 2, 28.10.2022

TRIAL DESIGN Overall design**Design:**

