4 STUDY VISITS AND PROCEDURES

Study timeline:

Information relating to study sent via letter		
Opportunity for self-enrolment, clinic enrolment, phone enrolment		A
Consent		B
Randomisation	Intervention	Control
Baseline data collection	C D E	C D E
3 months	F G H	F G
6 months	F G	F G
12 months	D E F G H	D E F G
A	Survey screening for inclusion/exclusion criteria sent to all potential participants	
B	Children meeting inclusion criteria and interested in study referred to PICF and consent form	
C	Demographic information (as part of the baseline questionnaire)	
D	Spirometry	
E	CFQ-R & EQ-5D-Y (as part of the baseline questionnaire)	
F	Data download from EPIC (admissions, LOS, contacts with CF team)	
G	Online follow up questionnaire	
H	Semi structured interviews	

Description of intervention

Remote symptom monitoring and automated treatment plans:

Participants randomised to the intervention arm will receive onboarding material (Appendix 7) detailing instructions of how to access and use the remote monitoring system via the RCH portal.

Participants will be asked to complete two surveys:

1. Baseline symptom survey (Appendix 8)

Participants will be prompted to complete survey by a push notification sent to their mobile phone and built into EPIC at the:

- Commencement of the trial;
- Each month post commencement of the trial; and
- After each exacerbation is detected.

2. Twice weekly symptom survey (Appendix 8)

Participants will be prompted to complete a survey by a push notification sent to their mobile phone and built into EPIC twice a week

The survey is a validated tool for detecting pulmonary exacerbations in people with CF[29].

A score is assigned to each survey field. Every symptom-monitoring questionnaire completed by the patient or patient's family is compared to their last known baseline questionnaire.

If the frequency or severity of **two or more symptoms** have worsened compared to baseline, the **Exacerbation Pathway** is triggered (Appendix 9 for exacerbation calculations).

If the system detects an exacerbation, it will send an automated treatment plan out to the patient and their caregiver including:

- Directions to commence a specific antibiotic
- Directions to change/or increase airway clearance and inhalation therapy.

Information regarding antibiotic, airway clearance and inhalation therapy prescription will be extracted from the participant's EPIC file.

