5 SAFETY MONITORING AND REPORTING

Adverse events (non-serious and serious) will be captured from the time of first administration of the intervention until conclusion of the intervention and all events will be followed until resolution or stabilisation.

Risks:

Risk/Benefit assessment

Known potential risks

- Increased burden of care to families by having to fill out the symptom surveys twice a week
 - o Survey will take approximately 3 minutes to fill out each time
- Participants not filling out the survey and therefore not gathering enough data to assess feasibility/effectiveness
- Increased workload for CF team without extra funding
 - o The pilot allows patients and families to directly contact the CF team which may increase contacts

Study Name: Acceptability, feasibility and impacts of remote symptom monitoring and automated treatment plans in children with Cystic Fibrosis (CF) on highly effective modulators: a pilot randomised controlled trial.

Protocol Number: 91117

Version & date: version 2, 28.10.2022

- The pilot may identify more pulmonary exacerbations compared to usual care which may increase contacts with CF team
- Underestimating/overestimating pulmonary exacerbations in patients leading to changes in treatment
 - Underestimating: the system may miss small exacerbations where families would normally self-initiate antibiotics and increase airway clearance, thereby undertreating
 - Overestimating: the system may over detect small exacerbations where families would normally not initiate antibiotics and increase physiotherapy, thereby leading to increased utilisation of antibiotics, however increased airway clearance may benefit the patient without clinical harm.

Known potential benefits

- It is well known that earlier detection and aggressive treatment of pulmonary exacerbations leads to better outcomes in people with CF
- Increased and clearer pathways of communication with CF team
- Continuous rather than episodic care
- Increased participant understanding of what an exacerbation entails
- Symptom monitoring storage in EPIC to help inform traditional CF clinic reviews and improving in-clinic efficiency
- Ongoing symptom monitoring helping to guide ongoing treatment decisions

Assessment of potential risks and benefits

- Underestimating/overestimating pulmonary exacerbations in patients leading to changes in treatment
 - Utilisation of a survey based on a validated survey

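### Family time in the cost analysis is limited to attending appointments and admissions, so intervention survey time and absence for illness at home are left out of a declared societal (family) perspective

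*Protocol*

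**What the plan says.** The protocol synopsis states the economic objective as "undertaking a health economic evaluation from healthcare and societal (family) perspectives". Under Outcomes and outcome measures it lists seven items (5a to 5g). Two describe what the family itself spends: 5e, "Travel time and costs for appointments and admissions", and 5f, "Caregiver time off work & patient time off school to attend appointments/admissions". Row 5 of the objectives table in Section 3 frames the family side as "costs/savings to families compared with accessing usual care". Hypothesis 4 in Section 3.1 is that the new model will "Be cost neutral compared to usual care".

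On the intervention, the synopsis says: "Intervention group participants will be asked to complete a symptom survey twice a week". Section 4 adds a baseline symptom survey at the start, "Each month post commencement of the trial; and" again after each detected exacerbation. Symptom surveys become daily once an exacerbation is detected. The intervention arm also keeps all of usual care, including the quarterly clinics. Section 5 gives the survey's length: "Survey will take approximately 3 minutes to fill out each time".

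Section 4 (Questionnaires) sends a follow-up survey to both arms at 3, 6 and 12 months. It asks for economic data, with time off work and travel costs as examples, and separately about the burden of the trial. Section 6 costs the new model from the protocol and budgets and brings in patient costs without listing their components.

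**The concern.** The model asks families to do regular monitoring at home, on top of their clinic visits. The family time items register time only when someone attends something. A family that avoids an urgent visit is credited with the time saved, but a family that completes two surveys a week for a year is recorded as having spent nothing on them. The protocol recognises this burden, since it heads the list of known risks in Section 5, but no listed cost outcome or analysis step takes it up.

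The same wording leaves out a parent staying home from work, or a child staying home from school, because of an exacerbation managed at home. A model meant to detect and treat exacerbations earlier could plausibly change that quantity.

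At stake are the cost-neutrality hypothesis and the two planned ratios, cost per exacerbation avoided and cost per QALY, when taken from the family perspective. Section 6 says the pilot is to inform the economic data collection of a full trial, so a narrow definition here could be carried forward.

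**Working it through.** The protocol gives no total for family time, so there is no figure to reproduce. The check is direct arithmetic on its own schedule.

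**Inputs**
- Routine symptom surveys: 2 per week for 12 months (synopsis) = 2 × 52 = 104.
- Baseline symptom surveys: 1 at the start + 12 monthly (Section 4) = 13, before any that follow an exacerbation.
- Time per survey: about 3 minutes (Section 5). This is stated for the twice-weekly survey; using it for the baseline survey is an assumption.
- After a detected exacerbation: daily surveys, with reassessment at day 10 to 14 (Section 4).

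**Routine survey time per intervention family, full completion**
- Symptom surveys: 104 × 3 = 312 min = 5.2 h.
- Baseline surveys: 13 × 3 = 39 min.
- Total: 351 min = 5.85 h a year, or 351 / 52 = 6.75 min a week.
- At 50% completion: 5.85 × 0.5 = 2.9 h.
- Across about 15 intervention families (an even split of the minimum 30): 15 × 5.85 = about 88 h.

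**Added by each detected exacerbation, up to reassessment**
- Extra surveys over d days = d − 2d/7, which is 7.1 for d = 10 and 10 for d = 14.
- Time: 7.14 × 3 = 21.4 min to 10 × 3 = 30 min. One baseline survey afterwards adds 3 min, giving 24.4 to 33 min.
- The number per year is not given. Assuming one: 6.3 to 6.4 h in total. Assuming three: 7.1 to 7.5 h.

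**Which home activities are both omitted and specific to the intervention**
- Surveys: yes. The control arm does not complete them, and completing one is neither an appointment nor an admission.
- Home lung function after a trigger: not clearly omitted. Section 4 has the respiratory laboratory book it as a telehealth appointment, so work or school time lost to it can fall under 5f. The EPIC data list in Section 4 also counts telehealth among outpatient appointments.
- Extra airway clearance: not specific to the intervention. Section 5 notes that families ordinarily step it up themselves in an exacerbation. The difference between arms is unknown.
- Absence for illness or treatment at home: omitted from 5f in both arms.

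**The case against.** The strongest reply is that the plan does not exclude survey time. The follow-up survey's economic examples are open-ended and its mention of time off work is not tied to appointments. Appendix 10, which holds the survey, is not among the documents at hand. Section 6 admits patient costs without restriction, and valuing them could be left to an analysis plan. This stands in part: the raw data may well be collected. But the outcome list does fix the family items, and fixes them to attendance. The burden question is named apart from the economic data, and nothing assigns home time to the cost analysis.

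A second reply is that under 7 minutes a week on a phone is small, need not cost any work or school time, and concerns one component of a secondary objective in a pilot where wide cost intervals are already expected. That is fair, and it limits the weight of the point.

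A reader might infer more: that family cost as a whole is biased in the intervention's favour, or that all the home care is uncounted intervention time. The documents do not support either. Quarterly clinics continue in both arms, so no scheduled visit is saved by design, and triggered telehealth appointments add countable items to the intervention arm. If earlier treatment shortens illness, as hypothesis 3 in Section 3.1 might lead one to hope, leaving out illness absence would work against the intervention.

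**Conclusion.** The point holds as a mismatch between the stated perspective and the items that measure it. Omitting survey time understates the intervention's family cost for that component, by about 5.9 h per family-year at full completion and 2.9 h at 50%. This rests on the 3-minute figure applying to baseline surveys and on 13 of these a year; any detected exacerbation raises it. Omitting illness absence affects both arms, by an amount and in a direction that the documents do not allow one to estimate. The net direction of bias in family cost is therefore unknown. No effect in money terms or on a conclusion has been shown. The change is worth making because a family-perspective claim of cost neutrality cannot rest on attendance time alone. The point does not touch the feasibility and acceptability objectives.

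**What to change.** 1. Reword 5f to cover caregiver time off work and child time off school for appointments (including telehealth), for admissions, and for illness or treatment at home. Ask it in both arms in the existing 3, 6 and 12 month survey.
2. Add intervention survey time as a family cost item: completed symptom and baseline surveys × 3 minutes, valued at the rate used for other caregiver time. The EPIC reports in Section 4 already count both kinds of survey.
3. Show the cost-effectiveness results with and without this item as one of the sensitivity analyses that Section 6 already plans.

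The cost is low: no new visit or data source, a line in the outcome list and one in the analysis, and perhaps one reworded survey item, depending on what Appendix 10 now asks. The downside is that the intervention's family cost rises slightly.
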